**Table 4. General Management of AE by Grade (refer to Table 4 for specific AEs)**

irAE Toxicity Grade	Withhold/ Discontinue	Action Taken With Respect to Epacadostat	Supportive Care (see also Table 4)
Grade 1	No action.	Not applicable.	Provide symptomatic treatment.
Grade 2	May withhold study treatment per investigator's discretion.	If AE resolves within 30 days, subject may restart at the same dose and schedule for epacadostat. For an AE that does not resolve within 30 days, consider reducing epacadostat 1 dose level.	Consider systemic corticosteroids in addition to appropriate symptomatic treatment.
Grade 3	Withhold study treatment until AE resolves to $\leq$ Grade 2. Discontinue if study treatment cannot be resumed within 30 days.	Restart epacadostat at reduced dose level except in the case of Grade 3 rash that resolves without oral steroids. If AE does not resolve to $<$ Grade 2 within 30 days after re-initiating study treatment or progresses again to grade 3 after initiating study treatment reduce epacadostat 1 dose level. Discontinue therapy for grade 3 pneumonitis.	Systemic corticosteroids are indicated in addition to appropriate symptomatic treatment. May use 1-2 mg/kg prednisone or equivalent per day. Steroid taper should be considered once symptoms improve to $\leq$ Grade 2 and tapered over at least 4 weeks in most cases.
Grade 4	Withhold study treatment until AE resolves to $\leq$ Grade 2. Discontinue if study treatment cannot be resumed within 30 days.	Restart epacadostat at reduced dose level if the AE resolves to $\leq$ Grade 2 or baseline. If there is recurrence of a Grade 3/4 AE with reduced dose of epacadostat, then discontinue participation in the study.	Systemic corticosteroids are indicated in addition to appropriate symptomatic treatment. May use 1-2 mg/kg prednisone or equivalent per day. Steroid taper should be considered once symptoms improve to $\leq$ Grade 2 and tapered over at least 4 weeks in most cases.

**Table 4: Specific Management of Adverse Events**

Adverse Event	CTCAE v4.03 Grade	Recommended Symptom Specific Management (to be used at discretion of treating physician)
Injection site reaction	1-3	Administer 325-650 mg acetaminophen po every 4-6 hours prn. Note: Maximum cumulative daily dose of acetaminophen is 4 grams daily due to risk of severe liver toxicity.
Injection site reaction	4	Hold study treatment until injection site reaction resolves
Rash	1-2	Supportive care including topical emollients, sun protection, consider topical steroids
Rash	3	Interrupt epacadostat, use topical corticosteroids, consider oral corticosteroids. When rash $\leq$ grade 1, taper steroids if used, then restart at reduced dose. If only topical steroids used, can restart at same or reduced dose when $\leq$ grade 1..
Rash	4	Interrupt epacadostat and start oral steroids. Continue until $\leq$ grade 1 and taper steroids. Once steroids $\leq$ 10mg/day, restart at reduced dose
Flu-like symptoms	1-3	Administer 325-650 mg acetaminophen po every 4-6 hours prn. Note: Maximum cumulative daily dose of acetaminophen is 4 grams daily due to risk of severe liver toxicity.
Headache	1-3	Administer 325-650 mg acetaminophen po every 4-6 hours prn. Note: Maximum cumulative daily dose of acetaminophen is 4 grams daily due to risk of severe liver toxicity.
Nausea/vomiting	1 or 2	Prescribe antiemetics per treating physician's recommendation
Nausea/vomiting	3 or 4	Interrupt study treatment. Prescribe antiemetics per treating physician's recommendation. Fluid and electrolytes should be substituted via IV infusion if indicated. When nausea/vomiting resolves to $\leq$ Grade 2 restart epacadostat at a reduced dose level.
Diarrhea/colitis	1	Subjects should be carefully monitored for signs and symptoms of enterocolitis (such as diarrhea, abdominal pain, blood, or mucus in stool, with or without fever) and of bowel perforation (such as peritoneal signs and ileus). Continue treatment with epacadostat, and initiate supportive care measures, which include drinking liberal quantities of clear fluids. If sufficient oral fluid intake is not feasible, fluid and electrolytes should be substituted via IV infusion. An antidiarrheal can be started.
	2	Interrupt study treatment if indicated, and initiate supportive care measures, which include drinking liberal quantities of clear fluids. If sufficient oral fluid intake is not feasible, fluid and electrolytes should be substituted via IV infusion. An antidiarrheal should be started. When diarrhea resolves to baseline, restart epacadostat at the same dose.

Adverse Event	CTCAE v4.03 Grade	Recommended Symptom Specific Management (to be used at discretion of treating physician)
	3 or 4	Interrupt study treatment. When diarrhea resolves to baseline, restart epacadostat at a reduced dose. Monitor subjects for signs and symptoms of enterocolitis (such as diarrhea, abdominal pain, mucus or blood in stool, with or without fever) and of bowel perforation (such as peritoneal signs and ileus). In symptomatic subjects, rule out infectious etiologies and consider endoscopic evaluation for persistent or severe symptoms. For recurrent or persistent Grade 3 or 4 diarrhea, consider further dose reduction of epacadostat, or study treatment discontinuation.
Pneumonitis	2	Interrupt study drug and initiate systemic corticosteroids. Taper as necessary. May return to study treatment if condition improves to ≤ Grade 1. Permanently discontinue if toxicity does not resolve within 12 weeks of last dose or if subject shows inability to reduce corticosteroid to ≤ 10 mg prednisone or equivalent per day within 12 weeks.
	3 or 4	Permanently discontinue study drug. Immediately treat with intravenous corticosteroids. Administer additional anti-inflammatory measures, as needed. Add prophylactic antibiotics for opportunistic infections in the case of prolonged steroid administration.
Type I diabetes mellitus (T1DM; if new onset, including diabetic ketoacidosis [DKA]) or ≥ Grade 3 hyperglycemia, if associated with ketosis (ketonuria) or metabolic acidosis (DKA)	3 or 4	Insulin replacement therapy is recommended for Type I diabetes mellitus and for Grade 3-4 hyperglycemia associated with metabolic acidosis or ketonuria. Evaluate subjects with serum glucose and a metabolic panel, urine ketones, glycosylated hemoglobin, and C-peptide.
Hypophysitis	2 or 3	Treat with oral corticosteroids. When symptoms improve to ≤ Grade 1, steroid taper should be started and continued over no less than 4 weeks. Replacement of appropriate hormones may be required as the steroid dose is tapered.
	4	Discontinue study drug. Treat with an initial dose of IV corticosteroids followed with oral corticosteroids. When symptoms improve to ≤ Grade 1, steroid taper should be started and continued over no less than 4 weeks. Replacement of appropriate hormones may be required as the steroid dose is tapered.
Hyperthyroidism or hypothyroidism	2	Thyroid disorders can occur at any time during treatment. Monitor subjects for changes in thyroid function (at the start of treatment, periodically during treatment, and as indicated based on clinical evaluation) and for clinical signs and symptoms of thyroid disorders. In hyperthyroidism, nonselective beta-blockers (eg, propranolol) are suggested as initial therapy. In hypothyroidism, thyroid hormone replacement therapy, with levothyroxine or liothyronine, is indicated per standard of care.

Adverse Event	CTCAE v4.03 Grade	Recommended Symptom Specific Management (to be used at discretion of treating physician)
	3 or 4	In hypothyroidism, thyroid hormone replacement therapy, with levothyroxine or liothyronine, is indicated per standard of care. In hyperthyroidism, treat with an initial dose of IV corticosteroid followed by oral corticosteroids. When symptoms improve to $\leq$ Grade 1, steroid taper should be started and continued over no less than 4 weeks. Replacement of appropriate hormones may be required as the steroid dose is tapered.
Hepatic	2	Monitor liver function tests more frequently until returned to baseline values (consider weekly or twice weekly if steroids are not initiated). Treat with IV or oral corticosteroids.
	3 or 4	Treat with intravenous corticosteroids. When liver chemistry tests improve to $\leq$ Grade 1, a steroid taper should be started and continued over no less than 4 weeks. For recurrent or persistent Grade 3 liver chemistry tests, consider further dose reduction of epacadostat (see Table 5 for epacadostat dose modifications), or study treatment discontinuation. For persistent Grade 4 liver chemistry tests, discontinue study treatment.
Hy's law case a	4	Permanently discontinue study therapy at the first occurrence of liver enzyme elevations meeting the criteria for Hy's law.
Renal failure or nephritis	2	Treat with oral corticosteroids.
	3 or 4	Treat with systemic corticosteroids. When severity of the event improves to $\leq$ Grade 1, steroid taper should be started and continued over no less than 4 weeks. For recurrent or persistent Grade 3 renal failures or nephritis, consider further dose reduction of epacadostat (see Table 5 for epacadostat dose modifications), or study treatment discontinuation. For persistent Grade 4 renal failure or nephritis, discontinue study treatment.

a Hy's law is defined as follows: 1. Aminotransferase elevation (ALT or AST)  $> 3 \times$  ULN; 2. Total bilirubin  $> 2 \times$  ULN, without initial findings of cholestasis (elevated serum ALP); 3. No other immediately apparent possible cause of aminotransferase elevation and hyperbilirubinemia, including, but not limited to, viral hepatitis, liver metastases, pre-existing chronic or acute liver disease, or the administration of other drug(s) known to be hepatotoxic. Permanently discontinue study therapy at the first occurrence of liver enzyme elevations meeting the criteria for Hy's law.

## 6.5 Management of Adverse Events Associated from Radiotherapy

Radiotherapy is delivered as a standard of care palliative regimen and radiotherapy related toxicities will be addressed using standard institutional practices. With palliative doses delivered in this trial we anticipate minimal adverse effects for the treatment of dermal, subcutaneous, nodal, or visceral lesions.

## 6.6 Guidelines for Dosage Modification and Treatment Interruption or Discontinuation

Dosing interruptions may be permitted in the case of medical/surgical events or logistical reasons not related to study therapy (e.g., elective surgery, unrelated medical events, subject vacation, and/or holidays). Subjects will be placed back on study therapy within 4 weeks of the scheduled interruption. The reason for interruption should be documented in the subject's study record.

Criteria for dose modification, treatment interruption or discontinuation are outlined in Table 3 and Table 4.

A dose of epacadostat may be held up to 30 days. Patients unable to resume epacadostat after 30 days due to toxicity will discontinue ERS therapy due to treatment intolerability. Epacadostat may be dose reduced for a given patient after the DLT window of phase 1 or at any time in phase 2. Criteria for dose reduction of epacadostat are outlined in Table 3 and Table 4. Dose levels of epacadostat for dose reductions are outlined in Table 5. The dose of epacadostat may not be reduced below 50 mg BID even if the MTD is determined to be 100 mg BID. Patients requiring dose reductions below 50 mg bid will discontinue ERS therapy due to treatment intolerability.

**Table 5: Dose Modifications of Epacadostat**

Dose level 1	Dose Level -1	Dose Level -2	Dose Level -3
300 mg BID	200 mg BID	100 mg BID	50 mg BID

If necessary, doses of SD-101 can be delayed up to 5 days, but must be given within the intended treatment week. If this is not possible, the dose will be skipped completely. Every attempt should be made to deliver at least 3 doses during the treatment period. If a dose is delayed, the following dose should be delivered during the next treatment week, a minimum of 5 days after the previously given dose. Subsequent doses in subsequent weeks should also be administered a minimum of 5 days after the previous dose. The dose may not be modified. If more than two consecutive doses are missed due to toxicity, the patient may continue ERS therapy, but will be labeled as having treatment intolerability.

The prescribed dose of radiotherapy can be reduced to no lower than 60% of the dose as specified per fraction in response to treatment related toxicity at the treatment lesion or prior to the onset of treatment to respect normal tissue tolerances as deemed necessary by the treating radiation oncologist. If a dose of radiotherapy is missed it can be administered later within the first week of therapy. Any radiotherapy fractions not delivered during the first week of therapy cannot be made up and those doses will be skipped. Patients unable to receive at least 60% of the prescribed radiotherapy dose due to treatment toxicity may continue ERS therapy but will be labeled as having treatment intolerance.

### 6.7 Treatment Tolerability

DLTs and any other treatment related adverse event requiring discontinuation of ERS therapy will be deemed treatment intolerance. Patients unable to resume epacadostat after 30 days due to toxicity will discontinue ERS therapy and will be labeled as having treatment intolerance. If more than two consecutive doses of SD-101 are missed due to toxicity the patient may continue ERS therapy but will be labeled as having treatment intolerance. Patients unable to receive at least 60% of the prescribed radiotherapy dose due to treatment toxicity may continue ERS therapy but will be labeled as having treatment intolerance. Epacadostat dose reductions will not be labeled as treatment intolerance but will be reported separately.

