Four milligrams of SD-101 will be delivered into the treatment lesion by intralesional injection on days 1, 8, 15, 22, and 29. On Day 1 biopsy will precede intralesional injection, RT, or epacadostat. Intralesional injections will be performed by palpation of the lesion or under ultrasound or CT guidance as indicated. For patients with a visceral treatment lesion Day 22 and 29 injections are optional. A visceral lesion can be used as the treatment lesion only if considered safe for serial intralesional injections. Visceral treatment lesions must be easily identified and accessible for image guided needle placement, carry minimal risk of bleeding or infection, and minimal risk of damage to the organ or surrounding tissues. For example, liver or adrenal lesions may be suitable candidate treatment lesions whereas lesions in the lung, bowel, or heart would not be.

A DLT is defined as any of the following that occur during the 30 day DLT period: grade  $\geq 4$  injection site reaction OR  $\geq$  grade 3 treatment-related non-hematologic toxicity (excluding injection site reactions) OR AST/ALT  $> 3 \times$  ULN with bilirubin  $> 2 \times$  ULN, OR pneumonitis that requires holding treatment  $> 14$  days. All toxicities at least possibly related to the investigational regimen will be considered treatment-related. Grade 3 rash will not be included as a DLT if there is no desquamation, no mucosal involvement, if it resolves without systemic corticosteroids by the next scheduled dose of epacadostat or 14 days, whichever is longer, and epacadostat dose intensity is maintained at 75% of planned dose during DLT period (i.e  $< 8$  days of dose interruption). If epacadostat dose intensity cannot be maintained at 75% of planned dose during DLT period as a result of toxicity of any grade this will also be deemed a dose limiting toxicity.

Table 1 describes the standard dosing rules that will be followed.

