**5. TREATMENT PLAN**

**Table 2. Treatment Plan**

Agent	Dose	Route	Frequency
Epacadostat	50 - 300 mg BID	Oral	BID throughout study period.
Radiation	4 - 24 Gy	External beam	3 fractions of 8 Gy, 5 fractions of 4 Gy, or 2 fractions of 2 Gy (cohort 2 only), delivered 12–96 hours apart during the first week of therapy.
SD-101	4 mg	Intratumoral	5 total doses 1 x weekly on days 1,8,15, 22, and 29 (Day 22 and 29 optional for visceral treatment lesions). First dose to be delivered prior to radiotherapy.

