## **5.2 SD-101**

### **5.2.1 Dosage, Administration, and Compliance**

SD-101 will be administered as a 4 mg dose to the treatment lesion through intralesional needle placement. Needle placement will be performed by palpation, ultrasound, or computed tomography guidance as indicated. 5 intralesional injections will be administered over a 5 week period on days 1, 8, 15, 22, and 29. The final two injections are optional for patients with visceral treatment lesions.

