**Table 10: Study Variables**

Endpoint	Variable	Measurement	Comment
Primary- Phase 1	MTD	CTCAE V4.03	Outlined in section 3. The maximum dose at which <2 of 6 patients experienced a DLT
Primary- Phase 1	DLT	CTCAE V4.03	Outlined in section 3. A DLT is defined as $\geq$ grade 4 injection site reaction OR $\geq$ grade 3 treatment-related non-hematologic toxicity (excluding injection site reactions) OR ORAST/ALT > 3 x ULN with bilirubin > 2 X ULN, OR pneumonitis that requires holding treatment > 14 days. Grade 3 rash will not be included as a DLT if there is no desquamation, no mucosal involvement, if it resolves without systemic corticosteroids by the next scheduled dose of epacadostat or 14 days, whichever is longer, and epacadostat dose intensity is maintained at 75% of planned dose during DLT period (i.e < 8 days of dose interruption). If epacadostat dose intensity cannot be maintained at 75% of planned dose during DLT period as a result of toxicity of any grade this will also be deemed a dose limiting toxicity.
Primary- Phase 2	Safety	CTCAE V4.03	
Primary-Phase 2	DCR (CR+PR+SD)	irRECIST	DCR is the endpoint for the Simon two-stage phase 2 study
Secondary- Phase 2	ARR	irRECIST	Objective response at unirradiated sites, the endpoint for measuring responses
Secondary- Phase 2	Treatment tolerability	CTCAE V4.03	Outlined in section 6.6. DLTs and any other treatment related adverse event requiring discontinuation of ERS therapy will be deemed treatment intolerability. Patients unable to resume epacadostat after 30 days due to toxicity will be labelled as having treatment intolerability. If more than two consecutive doses of SD-101 are missed due to toxicity the patient will be labeled as having treatment intolerability. Patients unable to receive at least 50% of the prescribed radiotherapy dose due to treatment

			toxicity will be labeled as having treatment intolerability.
Correlative	ORR	RECIST and irRECIST	
Correlative	PFS	RECIST and irRECIST	
Correlative	OS	RECIST and irRECIST	
Correlative	PBMC Immunophenotype	FACS	Blood
Correlative	PBMC gene expression	qPCR / Nanostring	Blood
Correlative	Systemic Cytokine Signature	Luminex	Serum
Correlative	Try/Kyn ratio	Mass spectrometry	Serum
Correlative	Tissue Immune Markers	IHC / IF	Tissue
Correlative	Tumor gene expression	qPCR / Nanostring	Tissue
Correlative	Mutational load	Whole exome sequencing/ RNA sequencing	Blood and Tissue
Correlative	T cell receptor diversity	TCR deep sequencing	Blood and Tissue

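### The SD-101 part of the tolerability endpoint cannot be triggered on a three-injection visceral course and misses two scattered patterns on five, so some patients who lose most injections to toxicity can count as tolerant

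*Combined protocol and SAP*

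**What the plan says.** Treatment tolerability is a secondary objective (1.2.2) and a secondary endpoint (section 3, Table 10). Section 10.1 measures it as the share of patients without an intolerance label.

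Section 6.7 gives several routes to that label:
- a DLT;
- a treatment-related event that forces discontinuation of ERS;
- failure to resume epacadostat after 30 days because of toxicity;
- receipt of less than 60% of the prescribed radiotherapy because of toxicity;
- for SD-101, the condition "If more than two consecutive doses of SD-101 are missed due to toxicity".

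Table 10 repeats the last one: "If more than two consecutive doses of SD-101 are missed due to toxicity the patient will be labeled as having treatment intolerability". The text under Table 5 in section 6.6 has the same threshold. None of the three places has a variant for visceral lesions, and none counts total doses or a share of doses.

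On the schedule, section 5.2.1 says "5 intralesional injections will be administered over a 5 week period on days 1, 8, 15, 22, and 29", and then "The final two injections are optional for patients with visceral treatment lesions". Table 2 adds "First dose to be delivered prior to radiotherapy", and section 3 says "On Day 1 biopsy will precede intralesional injection, RT, or epacadostat". For an injection that cannot be given in its week, section 6.6 says "If this is not possible, the dose will be skipped completely". The same paragraph sets a delivery aim, "Every attempt should be made to deliver at least 3 doses during the treatment period", but does not link it to the label.

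**The concern.** The endpoint should show, among other things, whether the intralesional part of the regimen can be delivered. The SD-101 criterion depends on the order of the missed doses, whereas the radiotherapy criterion beside it is a cumulative share. An order-based rule with a threshold of three needs a long enough course to be reachable, and the visceral option allows a course of three.

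Two gaps follow. A short visceral course may be unable to trigger the criterion at all. On the full course, a patient can fall below the protocol's three-dose aim without three misses in a row. If so, patients who lost most injections to toxicity can be reported as tolerant, and whether the label is within reach depends on the lesion site.

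**Working it through.** The documents state no expected tolerability rate, so there is no figure to reproduce. The check is an enumeration.

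**Inputs**
- Label threshold: a run of more than 2, so at least 3, missed doses (6.6, 6.7, Table 10).
- Planned doses: 5 on days 1, 8, 15, 22, 29. For visceral lesions 3 are required and days 22 and 29 are optional (5.2.1), so 3, 4 or 5 may be planned.
- Day 1 is treated as given. It starts study treatment and comes before radiotherapy (Table 2, section 3), so treatment toxicity cannot cause it to be missed.
- Skipped doses are not made up (6.6).

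**Enumeration.** With day 1 given and *k* doses planned, there are 2^(k−1) given/missed patterns.

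| Planned | Patterns | More than half lost | Of these, labelled | Not labelled (days lost) |
|---|---|---|---|---|
| 3 | 2² = 4 | 1 | 0 | 8, 15 |
| 4 | 2³ = 8 | 1 | 1 | none |
| 5 | 2⁴ = 16 | 4 + 1 = 5 | 3 | 8, 15, 29; and 8, 22, 29 |

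*Three planned.* The longest possible run after day 1 is 2, so 0 of 4 patterns can be labelled. The worst case has 1 of 3 received (33%).

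*Five planned.* Losing {8, 15, 22} or {15, 22, 29} gives a run of 3, and losing all four gives a run of 4. All three are labelled. Losing {8, 15, 29} or {8, 22, 29} gives a longest run of 2 and no label, with 2 of 5 received (40%), below the three-dose aim.

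**Do the other routes catch these patients?** Partly.
- Section 3 makes treatment-related non-hematologic toxicity of grade 3 or higher a DLT, apart from injection site reactions and a qualified rash exception. An injection site reaction is a DLT from grade 4.
- Epacadostat intensity below 75% in the 30-day window because of toxicity is also a DLT. Seven days off gives (30 − 7)/30 = 76.7% and eight gives (30 − 8)/30 = 73.3%, which agrees with the protocol's limit of fewer than 8 days.
- What remains is toxicity that stops SD-101 while epacadostat continues: injection site reactions below grade 4, lower-grade flu-like symptoms, or hematologic toxicity. Sections 6.6 and 6.7 expressly allow ERS to continue after missed injections.

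**Illustration only.** Assume each later dose is missed for toxicity independently with probability *q* (not in the documents). For five doses, the share of majority-loss patients left unlabelled is 2q³(1−q) / [4q³(1−q) + q⁴] = 2(1−q)/(4−3q). This is 1.8/3.7 = 49% at q = 0.1 and 1/2.5 = 40% at q = 0.5. For three doses it is 100% at any *q*. If patients who stop tend not to resume, the five-dose share would be lower.

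**The case against.** Four points on the other side have weight.

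1. **There is no separate visceral schedule.** Table 2 lists five doses with two optional. A visceral patient planned for four or five who stops after day 1 misses three or four in a row and is labelled. A reader might infer that the criterion is out of reach for every visceral patient. The documents do not support that; it holds only where days 1, 8 and 15 alone are planned. They also do not say whether an optional dose that is withheld counts as missed, and that ambiguity is itself part of the problem.

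2. **Other routes catch much of the serious toxicity.** The 30-day DLT window covers all five scheduled days. The table of specific adverse event management recommends symptomatic treatment for injection site reactions of grades 1 to 3 and a hold only at grade 4, which is already a DLT. This narrows the gap. It does not close it, because that table is to be used at the treating physician's discretion.

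3. **Pattern counts are not frequencies.** The two five-dose escapes need an omission, a resumption and a further omission. A reader might infer that the reported rate is overstated by a known amount, or that the injection is the component most often abandoned in visceral lesions. The documents give no omission rate and no visceral proportion, so neither follows.

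4. **The endpoint is descriptive.** No hypothesis or decision rests on it, and section 12.5 tabulates dose delays and premature discontinuation anyway. That limits the consequence, but the published tolerability percentage would still carry the gap.

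**Conclusion.** The point holds in a limited form. On a three-injection visceral course the SD-101 criterion labels 0 of 4 patterns and misses the one with 1 of 3 received. On five planned doses it misses 2 of the 5 patterns that leave fewer than three received. These patients can count as tolerant, but do not necessarily do so: it requires that toxicity stops SD-101 alone, no DLT occurs, epacadostat intensity stays at 75% or more, ERS is not discontinued and no other route in 6.7 applies.

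This rests on day 1 being given and, for the three-dose case, on optional doses not counting as missed when they were never planned. How often it would happen cannot be derived from the documents. The effect is confined to one secondary endpoint and its dependence on lesion mix. The change is worth making because it is cheap.

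**What to change.** For the endpoint label only, in sections 6.6, 6.7 and Table 10:
- Define SD-101 intolerance as receiving less than 60% of planned SD-101 doses because of toxicity, consecutive or not. This matches the radiotherapy share in 6.7.
- For visceral lesions, record the planned number (3, 4 or 5) at the start, and state that an optional dose counts as missed only if it was planned and withheld for toxicity.
- Report the rate also by visceral versus other treatment lesion.

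Effect: 1 of 3 (33%), 1 of 5 (20%) and 2 of 5 (40%) are labelled; 2 of 3 (67%) and 3 of 5 (60%) are not. With four planned, 2 of 4 (50%) is labelled and 3 of 4 (75%) is not. A simple cut at fewer than three doses would be less even: it would label 2 of 3 (67%) while passing 3 of 5 (60%).

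Two related items need reconciling in the same edit. Table 10 gives 50% for the radiotherapy label where 6.6 and 6.7 give 60%. For SD-101 the choice between these shares alters only the 2 of 4 case. Also, section 3, section 10.1 and Table 10 refer to 6.6 for the tolerability definition, while the full text stands in 6.7.

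Cost: wording in three places and one extra item recorded at the start for visceral lesions. The reported tolerability rate may be lower. Treatment rules, including the option to continue ERS, and the MTD, DLT rules and Simon design do not change.
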